According to Bouwmeester and Jongerling (2020), the MBD holds more power with groups of participants than single cases as outcomes in each phase are averaged. The revised “quality rating scale for [the] Risk of Bias in *N*-of-1 Trials” therefore argues a minimum of five datapoints at baseline (Tate et al., 2013, p. 619). This improves monitoring of the level, trend, and variability of data, which is important if attrition is high (Kratochwill et al., 2010). The baseline length will range from five to seven weeks.

Attrition is problematic when participant dropout causes less than five datapoints at baseline or occurs at a critical timepoint (e.g., during the intervention) (Kratochwill et al., 2010). Attrition at each stage will be reported in a flow chart, as per the Reporting Standards for Research in Psychology (APA, 2008).

The risk of attrition will be mitigated using a two-phase AB design, whereby A is the baseline (control), and B is the intervention (Levin et al., 2021). The longevity of change will be monitored three- and six-months post-intervention, reducing study demands compared to an ABA design where the second A acts as another control (Kazdin, 2021). Six-month follow-ups may occur after thesis submission for the purpose of publication if recruitment presents a challenge.

Participants

Nine adult stroke survivors will be recruited via NHS services (e.g., Early Supported Discharge Stroke Teams, IAPT services) and stroke charities. In SCEDs, six participants are recommended (Kratochwill et al., 2013), though nine will be recruited to account for attrition, with three being assigned to each baseline length (five, six, or seven weeks).

Inclusion

Adults (>18 years) will be included if they have:

- Suffered a stroke over three months ago.
- No other neurological illness.
- Not currently receiving any psychological intervention.
- No severe communication difficulties.
- No severe cognitive impairments.
- No current or historical suicidal ideation/self-harming behaviours.
- Not been diagnosed with major long-term health conditions in the last 12 months (except for stroke or trans-ischaemic attack; TIA).
- Access to a device with a camera, stable internet connection and private space.

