Inclusion criteria ensure any changes are due to the intervention and not other factors such as spontaneous recovery from stroke which typically occurs within the first three months (Cassidy & Cramer, 2017; Zeiler, 2019); and other rehabilitative or psychological programmes. Criteria also ensures the monitoring of post-stroke adjustment rather than adjustment to other health conditions.

Exclusion

Participants will be excluded if they have:

- Had a TIA without the presence of a stroke.
- No current distress around adjusting to the consequences of stroke.

- Distress of a severity that it cannot be managed safely in a group therapy setting

Distress will be assessed using the Clinical Outcomes in Routine Evaluation – 10 (CORE-10) as it is considered valid and reliable in UK primary care populations (Barkham et al., 2013).

Measures

Outcome measures will be completed weekly, pre- and post-intervention or at three- and six-month follow-ups to reduce participant burden associated with frequent questionnaire completion. This is important as attrition is more likely amongst stroke survivors if studies are time-consuming (Weerasekara et al., 2021).

Less frequently collected measures were decided based on the secondary gains of ACT, the importance for between-study comparisons in assessing intervention efficacy and the second aim of feasibility and acceptability.

While some measures are not validated post-stroke, Bouwmeester and Jongerling (2020) suggest that the repeated collection of data in a SCED provides increased reliability in the test statistic.

CompACT-10

The Comprehensive assessment of Acceptance and Commitment Therapy Processes (CompACT) assesses PF (Francis et al., 2016) from the “three dyadic ACT processes”: openness to experience (OE), behavioural awareness (BA) and valued action (VA) (Golijani-Moghaddam et al., 2023, p. 60). The CompACT-10 (not attached due to copyright) has 10 items with acceptable to excellent internal consistency (Cronbach’s alpha, α , “total = 0.81, OE = 0.70, BA = 0.79, and VA = 0.75”), test-retest reliability (intraclass correlations, ICC, total = 0.83; OE = 0.86; BA = 0.76; VA = 0.89), convergent validity with the acceptance and action questionnaire-II ($r_s = -0.65$ and -0.70) and concurrent validity with

measures of wellbeing ($r_s = 0.66$ and 0.67) amongst UK-representative samples (Golijani-Moghaddam et al., 2023, p. 64).

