Higher scores indicate greater PF (Golijani-Moghaddam et al., 2023) and will be completed weekly during baseline/intervention phases and repeated at follow-up.

Community Integrated Questionnaire (CIQ)

The CIQ has 15 items assessing participation in relation to three subscales: home/social integration and productivity (Wilier et al., 1994). Each item has a three-point scale and is totalled for an overall score, whereby higher scores indicate greater independence for activities such as managing finances, housework, employment/volunteering and socialising (Dalemans et al., 2010). Data will be collected pre/post-intervention and at follow-up.

The CIQ has high test-retest reliability ($ICC = 0.997$) amongst geriatric populations (Singh & Sharma, 2015) and good internal consistency ($\alpha = 0.71 - 0.84$) and test-retest reliability ($ICC = 0.91-0.97$) amongst adults with neurological conditions (Turcotte et al., 2019). The measure has also been extensively used in stroke research (Lee et al., 2015; Matos et al., 2020; Sathananthan et al., 2022).

Clinical Outcomes in Routine Evaluation-10 (CORE-10)

The CORE-10 is a 10-item questionnaire assessing psychological distress that is considered valid and reliable in UK primary care populations (Barkham et al., 2013). Each item is rated on a 5-point Likert scale from 'not at all' to 'most or all of the time' and provides a total clinical score where higher scores are indicative of more severe psychological distress (Barkham et al., 2013).

Amongst a post-acute stroke sample, the CORE-10 was considered to have high internal consistency ($\alpha = 0.80$) and test-retest reliability ($ICC = 0.81$) as well as acceptable

concurrent validity with measures of depression and anxiety ($r = 0.49 - 0.89$) (Steverson et al., 2024).

Aside from its validity and reliability, the CORE-10 was chosen due to its wide use in research and clinical settings, allowing for between-study comparisons and monitoring of wellbeing for early signposting (see 'Ethics: Risk Management'). This data will be collected pre/post-intervention and at follow-up.

Stroke-Specific Quality of Life (SS-QoL)

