A poster will be circulated via NHS services and stroke charities, containing a link to an online survey (JISC, 2021). Here, participants can view the information sheet, consent form, and eligibility questionnaire. A consent to contact form and researcher contact details will be available should anyone prefer discussing the study before consenting to participate. To ensure accessibility to the study, the consent to contact form can be signed by the individual themselves or, if unable to sign (for example, due to physical impairment following stroke preventing ability to write, or due to healthcare appointments being held remotely), they can provide verbal consent to be contacted by the researcher to their clinician. The clinician can then sign the consent to contact form on their behalf.

Those meeting the inclusion criteria will attend a 30-minute video call to confirm eligibility, including ability to use videoconferencing platforms as per guidance for remote research (McCarthy et al., 2021). Guidance for accessing video calls will be provided.

Once a group is identified, participants will be randomly allocated to a baseline length (five, six or seven weeks) and provided a start date. Visual calendars will mark the dates of

each phase/task. Reminders and links to the questionnaire will also be sent weekly. During baseline and intervention phases, the CompACT-10 (Golijani-Moghaddam et al., 2023) will be completed weekly.

The intervention, delivered by the research team, lasts eight weeks. Each session is two hours, including breaks. Permission to access the protocol for the modifications to the intervention was granted (Large et al., 2019) and has been received. ACT training will be sought for the chief investigator prior to the study commencing.

Participants will have time at the end of each session for group reflections with reminders of where to access mental health support.

Immediately before and after the intervention phase and at three- and six-month follow-ups, participants will complete all questionnaires. At six-months, a 30-minute debrief will be offered.

As per the BPS Code of Human Research Ethics (BPS, 2021), all participants will receive a £10 gift card as reimbursement for their time.

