Individuals will not be pressured into participating. All aims of the study will be provided prior to consenting. Participants will be reminded of their right to withdraw without explanation at the start of each questionnaire and intervention session.

Participant Distress and Burden

Questionnaires will be as short as possible and PPI will inform the accessibility of all supporting documents, reducing the potential for distress/burden from the point of advertisement and throughout.

While there is preliminary evidence of ACT improving mood post-stroke (Graham et al., 2015; Majumdar & Morris, 2019; Ooi & Steverson, 2023; Rauwenhoff et al., 2023; Sathananthan et al., 2022), potential risks will be highlighted during recruitment to improve feelings of preparedness and reduce the likelihood of distress.

Criteria of no severe cognitive impairments or communication difficulties will ensure participants can engage with the demands of the study, keeping distress and burden to a minimum. Excluding those without access to a private space during the intervention will reduce the likelihood of conversations being heard by those not participating and the associated distress this may cause for both participants and bystanders.

To minimise distress and burden during questionnaire completion and the intervention, breaks will be provided/encouraged. Group rules will encourage participants to be mindful of the sensitive nature of topics discussed and therefore how much they share with the group about their personal experiences.

Risk Management

Prior to consenting to participate, contact details for mental health services/charities/helplines will be provided at the end of the information sheet. This information will be re-sent with the questionnaires, during each session and at follow-up.

When assessing eligibility, individuals will be excluded if they have a history of complex mental health difficulties to ensure participants can engage with the content of the questionnaires and intervention. This will reduce the likelihood of sensitive topics of suicide in the group setting, further reducing the potential for participant distress.

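### Other psychological therapy is checked only at entry and not recorded afterwards in the available text, so the uncontrolled three- and six-month scores cannot be separated from later therapy when read as longevity of change.

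*Combined protocol and SAP*

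**What the plan says.** **Control of other therapy.** The Inclusion list requires that participants are "Not currently receiving any psychological intervention". The paragraph after that list gives the purpose: "Inclusion criteria ensure any changes are due to the intervention and not other factors". The factors it names are spontaneous recovery "and other rehabilitative or psychological programmes".

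**Signposting.** Under Ethics, Risk Management, "contact details for mental health services/charities/helplines will be provided at the end of the information sheet", and then "This information will be re-sent with the questionnaires, during each session and at follow-up". Under Procedure, each session closes with group reflection "with reminders of where to access mental health support". The CORE-10, an outcome measure, was chosen partly because it allows "monitoring of wellbeing for early signposting". Recruitment routes include IAPT services, and people with no current adjustment distress are excluded.

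**Follow-up.** Under Design, "The longevity of change will be monitored three- and six-months post-intervention". The same paragraph chooses AB over ABA to reduce demands on participants, so there is no second control phase. Under Procedure, all questionnaires are repeated at three and six months. The Analysis section applies the RCI to pre- versus post-intervention scores and gives no rule for interpreting follow-up scores.

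**The concern.** The plan itself treats other psychological therapy as a competing explanation and says that its criteria remove it. A criterion met on the day of screening cannot do that for scores taken months later. Participants enter distressed, know where to find help and are reminded of it regularly, so some may start counselling or another talking therapy before the last assessment.

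At stake is the longevity statement. If a participant's gain has faded and later therapy restores it, the six-month score looks like lasting ACT benefit. Without a record of the therapy and its date, nobody reading the plots could recognise that case, and the information is hard to recover reliably afterwards.

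**Working it through.** The plan gives no figure to reproduce on this point. The check is a reading of the text, followed by an illustration.

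**1. What covers each period**

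| Period | Length | Safeguard against other therapy |
|---|---|---|
| Eligibility | one occasion | Inclusion criterion |
| Baseline | 5 to 7 weeks | none recorded; randomised staggered start, weekly CompACT-10 |
| Intervention | 8 weeks | none recorded; staggered start, weekly CompACT-10 |
| Follow-up to six months | about 26 weeks | none recorded; no control phase, assessed only at three and six months |

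Shortest span from start of baseline: 5 + 8 + 26 = 39 weeks. Longest: 7 + 8 + 26 = 41 weeks. Baseline lengths are allocated only once a group has been formed, so the time since eligibility is somewhat longer. Follow-up makes up 26/41 = 63% to 26/39 = 67% of the span, and it is the part with the fewest measurements and no design protection.

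**2. What can and cannot be seen in the data**

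- *Flat intervention phase, then improvement at follow-up.* The weekly scores and the immediate post-intervention battery would show this as change that arose after the group ended. It would not pass as maintenance, though its cause would still be unknown.
- *Improvement, relapse, other therapy, recovery.* If the relapse falls between assessments, the post, three-month and six-month scores look level. Nothing collected distinguishes this from maintained benefit.
- *Improvement, then other therapy without relapse.* The score is also level, and the contribution of ACT alone cannot be identified.

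**3. Illustration of how often a case might arise**

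The documents give no uptake rate. Let p be the assumed chance that a participant starts other therapy after entry and before the six-month assessment, independently of the others. Then P(at least one) = 1 − (1 − p)^n. The two sample sizes come from the Participants section: nine to be recruited and six recommended.

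| p (assumed) | n = 9 | n = 6 |
|---|---|---|
| 5% | 1 − 0.95^9 = 37% | 1 − 0.95^6 = 27% |
| 10% | 1 − 0.90^9 = 61% | 1 − 0.90^6 = 47% |
| 20% | 1 − 0.80^9 = 87% | 1 − 0.80^6 = 74% |
| 30% | 1 − 0.70^9 = 96% | 1 − 0.70^6 = 88% |

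One such participant is 1/9 = 11% to 1/6 = 17% of the follow-up evidence. These figures count people. They say nothing about how far any score moves, so they do not measure bias.

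**The case against.** The strongest reply is that follow-up is only monitoring. The aim is preliminary efficacy, the described analyses centre on baseline versus intervention and pre versus post, and the plan openly gives up a second control phase. Nothing says that the six-month scores will be credited to ACT alone. This stands in part: it limits the weight of the point. It does not remove it, because the plan calls the follow-up a check on longevity and says its criteria exclude other psychological programmes as a cause of change.

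A reader might infer more than the documents support:

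- *That the bias runs towards durability because those who did not benefit seek help.* This is plausible, but no passage supports it. Direction and size are unknown.
- *That later therapy would turn a non-responder into a maintained responder.* The weekly intervention scores would show there was no change to maintain.
- *That the main comparison is compromised.* The randomised baseline lengths and weekly scores make it less exposed, although therapy started in those weeks would also go unrecorded.
- *That signposting is the fault.* It is a safety measure; the gap is in the record.

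Two further objections are fair. Part of the document between Procedure and the patient and public involvement feedback was not available, and the survey forms are not reproduced, so a therapy question may exist there; nothing in the available text points to one. Medication, physical rehabilitation and life events could also affect uncontrolled follow-up. Psychological therapy is singled out here because the plan names it and says it is ruled out.

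**Conclusion.** The point holds in a limited form. The plan's assurance about other psychological programmes is true of status at entry and cannot extend over the following 39 to 41 weeks or more. On the available text, a three- or six-month score affected by later therapy could not be identified, so those scores cannot be read as longevity of the ACT change without qualification.

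The size of any bias cannot be stated. The chance of at least one affected participant (37% to 96% of nine, 27% to 88% of six) rests wholly on an assumed 5% to 30% uptake and on independence between participants. The conclusion does not depend on that range. It needs only that later therapy is possible and unrecorded, and that follow-up has no control. This is a worthwhile, low-cost improvement to data collection and reporting, and it is no challenge to the central comparison.

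**What to change.** 1. Add one dated item to the pre-intervention, post-intervention, three-month and six-month batteries: has any psychological therapy been started since the last full questionnaire (at the pre-intervention battery, since eligibility was confirmed), and if so what and when? Put it in the questionnaires that carry initials, since the feedback questionnaire is anonymous and could not be linked to a plot.
2. Mark each start on that participant's plot.
3. State in the Analysis section that follow-up will be reported for all participants as an uncontrolled observation, with affected cases identified.
4. Reword the statement after the Inclusion list so that it claims only that participants were not in other psychological therapy at entry.
5. If a result using only scores obtained before other therapy is shown, present it only beside the full result, and warn that it selects on an event after treatment, may drop non-responders and so may flatter durability.

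Signposting and clinical care are unchanged. The cost is one question at four time points, a few sentences in the plan, and slight extra burden. The two people consulted took 5 to 10 minutes over the 48-item questionnaire, so one item should add little, although fatigue was raised as an issue in that consultation.

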Title: ACT for Post-Stroke Adjustment Via Telerehabilitation

Date Study Approved by REC: 23rd June 2025

Protocol Version 3 Date: 29th July 2025

Protocol Amendment Approval Date: 2nd September 2025

NCT Number: Pending

ACT for Post-Stroke Adjustment Via Telerehabilitation

Aims

The primary aim is to assess the preliminary efficacy of an adapted eight-week group of acceptance and commitment therapy (ACT), developed following Majumdar and Morris' 2019 study, that is delivered via telerehabilitation using idiographic methods.

The second aim is to explore the preliminary feasibility and acceptability of the intervention for adult stroke survivors.

Background

Stroke

With more than 1.3 million stroke survivors in the UK, stroke is considered one of the UK's main causes of disability (Stroke Association, 2017). The risk of stroke increases exponentially with age (Truelsen et al., 2006), but can have a detrimental impact on an individual's life regardless, affecting social interactions (Vickers, 2010), mood (Hilari, 2011) and activities of daily living (Hilari, 2011; Lazar & Boehme, 2017). Changes can be unexpected and difficulty adjusting could get in the way of rehabilitation (Mahmoud & Elaziz, 2016), affecting quality of life (QOL) (Bays, 2001; Jeong et al., 2012). Consequently, stroke survivors identify improvements to mental health services as an important research area (Weerasekara et al., 2021), and psychological intervention for wellbeing and adjustment is within the top 10 priorities for stroke rehabilitation (JLA, n.d.).

According to NICE (2023) Guidelines for psychological functioning in stroke rehabilitation, clinicians should assess changes to the way individuals adjust and cope, including monitoring of emotional functioning and behaviour. Specifically, Acceptance and commitment therapy (ACT) is recommended for those most at risk of anxiety or depression post-stroke (National Clinical Guideline for Stroke, 2023).

Acceptance and Commitment Therapy

ACT is a psychological intervention (Harris, 2019; McHugh, 2011) aiming to alter how individuals relate to distress following unexpected changes in circumstance, rather than change the distress itself (Hayes et al., 2006). ACT is therefore favoured for promoting wellbeing in adults living with long-term health conditions, including brain injury (Sander et al., 2021), chronic pain (Hughes et al., 2017), and multiple sclerosis (Han, 2021).

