SS-QoL measures health-related QOL amongst stroke survivors (Vincent-Onabajo et al., 2016). The 12-item version refers to domains of self-care, mobility/upper extremity, language, vision, thinking, work/family/social roles, personality and mood/energy which are rated on a five-point scale to generate a mean total score and physical and psychosocial sub-scores (Post et al., 2011). The measure has good internal consistency ($\alpha = 0.77 - 0.89$) (Post et al., 2011) and is validated in a bi-ethnic stroke population (Kerber et al., 2013).

Higher mean scores indicate better QOL (Vincent-Onabajo et al., 2016). Data will be collected pre/post-intervention and at follow-up.

Short Warwick Mental Wellbeing Scale (SWEMWBS)

SWEMWBS is a seven-item questionnaire that monitors mental wellbeing (Stewart-Brown et al., 2009). Each positively phrased item is ranked on a Likert-scale of one (none of the time) to five (all of the time) and totalled to provide an overall score, whereby higher scores indicate better mental wellbeing (Stewart-Brown et al., 2009). The scale has been validated across clinical (Shah et al., 2021; Vaingankar et al., 2017) and non-clinical populations (Ng Fat et al., 2017), and is comparable to the 14-item version (Ng Fat et al., 2017). SWEMWBS is also considered responsive to change following therapeutic intervention at a group and individual level (Shah et al., 2018).

Beyond assessing mental wellbeing, the scale also assesses cost effectiveness of an intervention in regard to its impact on wellbeing and quality of life (HACT, 2017). Therefore, data will be collected pre/post-intervention and at follow-up.

Feasibility and Acceptability

Immediately after the intervention, participants will complete a questionnaire created for the purpose of this study to address the second aim on intervention acceptability. No gold standards for satisfaction scales currently exist, but they typically include satisfaction and staff skills (Miglietta et al., 2018).

Feasibility will be assessed using six criteria monitoring attrition, attendance and homework completion, as per previous research (Sathananthan et al., 2022).

Procedure

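### Acceptability is asked once, after the eight-week intervention, with no stated way of reaching participants who stop early, so it may be overstated

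*Combined protocol and SAP*

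**What the plan says.** The Aims section states: "The second aim is to explore the preliminary feasibility and acceptability of the intervention for adult stroke survivors". Under Measures, Feasibility and Acceptability, the acceptability half has one instrument and one time point: "Immediately after the intervention, participants will complete a questionnaire created for the purpose of this study". The Procedure section gives the length: "The intervention, delivered by the research team, lasts eight weeks".

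The same part of Measures assesses feasibility separately, with six criteria covering attendance, homework and attrition. The Design section adds that losses at each stage will be shown in a flow chart.

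Loss is expected. The Participants section says "In SCEDs, six participants are recommended" and that "nine will be recruited to account for attrition". The Design section treats dropout during the intervention as critical, and the Measures section notes that stroke survivors are more likely to leave studies that take up a lot of time.

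Under Ethics, Informed Consent, participants can withdraw whenever they wish and need not say why. The account of patient and public involvement (Questionnaire Completion) says that the feedback form carries no initials, so that people can criticise freely. It also offers an optional conversation with the research team, mentioned at the start of that same form.

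**The concern.** People who start the group and stop are likely to know most about what was hard to accept in it. Burden is a reason for leaving that the plan itself foresees, and burden is also part of acceptability, so whether a rating is missing may depend on what the rating would have been. The available text describes no exit form, no acceptability question during treatment and no step to seek leavers' views. The optional conversation does not fill the gap, because it is offered within the form that leavers may never see.

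What is at stake is the acceptability half of the second aim, which is also part of the second research question. With nine participants, two or three unheard views can change the picture, and they are hard to recover once people have gone.

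A related, smaller gap concerns the Reliable Change Index, which needs a pre-intervention and a post-intervention score. The Analysis section does not say how a starter without a post score will be shown.

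**Working it through.** **1. The plan's sample size.** Three baseline lengths × three participants = 9, as stated. No dropout rate is given, but one can be inferred from the recommended six. Using n = 6/(1 − d), rounded up:

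- d = 10%: 6/0.90 = 6.67, so 7
- d = 20%: 6/0.80 = 7.5, so 8
- d = 25%: 6/0.75 = 8
- d = 30%: 6/0.70 = 8.57, so 9
- d = 1/3: 6/0.667 = 9

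Nine therefore leaves room for up to three losses (3/9 = 33%) before the number falls below six. This is a tolerance implied by the figures, not a forecast in the plan.

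**2. What unheard leavers could do to the result.** Assumptions, none of them from the plan: acceptability is summarised as satisfied or not; all nine start the intervention; k of them stop and give no rating; s of the 9 − k completers are satisfied.

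- Completers only: s/(9 − k)
- All starters, if every leaver was dissatisfied: s/9
- All starters, if every leaver was satisfied: (s + k)/9

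With every completer satisfied (s = 9 − k):

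| Leavers k | Completers only | All starters | Largest possible overstatement |
|---|---|---|---|
| 0 | 9/9 = 100% | 100% | 0 points |
| 1 | 8/8 = 100% | 8/9 = 89% to 100% | 11 points |
| 2 | 7/7 = 100% | 7/9 = 78% to 100% | 22 points |
| 3 | 6/6 = 100% | 6/9 = 67% to 100% | 33 points |

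**3. The direction is not fixed.** With three leavers and one dissatisfied completer, the completer figure is 5/6 = 83%. The all-starter value then lies between 5/9 = 56% and (5 + 3)/9 = 89%, so the completer figure could be slightly too low.

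**4. The timing of losses matters.** People lost during the five- to seven-week baseline never receive the intervention and cannot rate it. Take three losses in all and six satisfied completers:

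- one loss in baseline: eight starters, lower limit 6/8 = 75%
- two losses in baseline: seven starters, lower limit 6/7 = 86%
- three losses in baseline: six starters, 6/6, no gap

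**5. Sampling error.** The exact (Clopper-Pearson) 95% interval for 6/6 is 54% to 100%. The figure is imprecise even before selection is considered, and the interval makes no allowance for people who were not asked.

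**The case against.** The strongest reply is that the text is silent rather than wrong. It says participants will complete the form, not only those who finish; links go out by text and email; and someone who stops attending without withdrawing might well be sent it. Part of the document was also unavailable for review. This stands in so far as it rules out saying that leavers are excluded. It does not close the gap, because nothing available says that they are included.

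Second, leavers are already counted through the feasibility criteria and the flow chart, so a reader will see acceptability beside attrition. This stands, and it limits the point to acceptability. A count shows how many left, not what they thought of the group.

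Third, the plan sets no acceptability percentage or threshold, and the form also seeks comments and suggestions. This stands too: the percentages above illustrate sensitivity and do not predict a planned result.

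A reader might go further and infer that the share of participants with reliable improvement will be inflated in the same way. The documents do not support that. The plan presents individual pre-post change in a modified Brinley plot and commits to no responder proportion. The weekly CompACT-10 also supplies data for the visual and non-overlap analyses up to the point of leaving.

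Finally, a form triggered when one person out of nine stops could identify that person by its timing. This is a fair cost, which the fix has to handle.

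**Conclusion.** The point holds for acceptability only. With one measurement after the intervention and no stated route to early leavers, the acceptability result may be overstated. In the illustration with nine starters and three leavers, 100% among completers is compatible with 67% to 100% among all starters. The 67% is a worst case: all three losses come after treatment begins, and all three leavers are dissatisfied. With fewer such losses the range narrows, and with none it disappears.

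A reader might infer that the second aim as a whole is biased upwards. The documents do not support this. Feasibility is half of that aim and already counts those who leave. For acceptability, an upward direction is likely but not established, since people may leave for unrelated reasons, may have been satisfied, or may be sent the form after all. This is a low-cost improvement to an exploratory study, not a defect that undermines it.

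**What to change.** - State that the same voluntary, anonymous form will be offered to everyone who starts the intervention, including those who stop, with no reason required. It should not go to anyone removed for loss of capacity or anyone who has asked not to be contacted; they stay in the denominator as non-responders.
- Send it to leavers on the common end-of-intervention date, so that their replies arrive with the others. If it is sent when they stop, tell them that timing may make them identifiable.
- Report the number responding out of the number who started, and read acceptability beside attrition and attendance. This needs only a count, so the form can stay without initials.
- Keep inviting those who stop sessions but remain in the study to complete the weekly and post-intervention measures. When presenting reliable change, state how many starters have no post score.

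The cost is a few sentences in the protocol and the use of an online form and message links that already exist. Some leavers will not reply, so the gap narrows rather than closes. Anonymity is slightly weaker in so small a group, and the figures may look less favourable.
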